#### 9.4.2 ANALYSIS OF THE PRIMARY ENDPOINT(S)

We updated our analysis plan on 1.30.24 since two sites recruited only one participant. We wanted to make use of the data from their matched pairs rather than having to drop 4 sites from our analyses. Thus, to increase the efficiency of our matched pair design and maximize data utilization from all sites we will not account for the matching of clusters in our analyses.

We will test differences between treatment groups in the proportion of participants who are engaged and retained in treatment using generalized linear mixed models (GLMM). GLMM models will include a random effect for site to account for potential positive correlations among observations within sites and will evaluate the fixed effect for the interventions. For the PAM outcome, we plan to conduct linear mixed models, where the response variable will be the PAM score at the week-36 assessment and at 3-months post-partum. Models will include a random effect for site and will evaluate fixed effects for the interventions and baseline PAM scores. If assumptions of normality are violated, we will consider transformations or alternative distributions to determine the model with the best fit. Due to the small number of samples, we will use small sample corrections in our mixed models. For continuous outcomes we will use Satterthwaite's degrees of freedom approximation given the small number of clusters and high variability in size of clusters in our study. For binary outcomes we will use restricted pseudo-likelihood with between-within correction to the degrees-of-freedom.

#### 9.4.3 ANALYSIS OF THE SECONDARY ENDPOINT(S)

To tests differences in secondary patient outcomes between care models groups, we will use GLMM as described above.

Our co-Investigator, [name] will collect and analyze qualitative data. Qualitative interviews will be will be audio recorded, transcribed, and independently coded by two trained masters level researchers who will be supervised by [name]. All transcripts will be de-identified. The team will develop codes to be used in the content analysis(102, 103) and utilize these codes to identify themes related to deployment of the two models. Themes will be examined both within and across informant groups. The team will use NVivo (104) to analyze data. Subsequent to the initial training, two staff will independently code each transcript and meet together with [name] to compare codes, discuss and work towards consensus in order to build a common understanding and use of codes.(105) [name] will review interrater reliability on a regular basis in order to prevent coder drift and will retrain staff as needed. The collection of data from multiple informants, iterative process of data collection and analysis and use of two researchers to code transcripts, increases creditability, transferability, dependability, and confirmability of the findings.(105, 106)

#### 9.4.4 BASELINE DESCRIPTIVE STATISTICS

Differences between care models in baseline demographic and clinical characteristics will be assessed using chi-square tests for categorical variables and t-tests for continuous variables, or their non-parametric counterparts if the assumption of normality is not met.

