## 4 STUDY DESIGN

### 4.1 OVERALL DESIGN

Yale will lead this study to compare the effectiveness of two models of support for reproductive health clinicians who will provide prenatal and addiction care for pregnant and postpartum women with an opioid use disorder in obstetrical centers in Connecticut and Massachusetts. The two models being compared are: 1) a collaborative care (CC) approach, based upon the Massachusetts Office-Based-Opioid Treatment Model, that would provide onsite training, and support to providers through the use of a care managers; and 2) a tele-support approach modeled on the Project Extension for Community Healthcare Outcomes (ECHO), a remote education model that provides mentorship and guided practice and participation in a learning community via video conferencing. Twelve obstetrical centers who currently do not have a system in place to treat pregnant women with OUD will be recruited and their characteristics matched. The unit of randomization is the obstetrical center. We will randomly assign one center in each pair to either the CC or ECHO model, 6 sites to each model of support. A statistician, blinded to the identities of the clinics, will assign a number to each clinic using a random number generator; within each matched pair, the clinic with the lower number will be assigned to CC and the other will be assigned to ECHO. Among the centers, we would recruit 264 women in total, 132 women from the CC sites and 132 from the ECHO sites, about 20 per site among the 12 sites.

Although we will recruit centers that report caring for at least 40 women per year who have an OUD, we will need an accurate method for estimating the rate of opioid use in order to compute outcomes. we will obtain the base rate of opioid and other illicit substance use in each practice by obtaining urine drug screens from all women attending the obstetrical practice for a prenatal visit in a one-week period. Urine collection will be anonymous and will use a small portion of the sample women typically provide at each prenatal visit. Clinic staff will collect urine samples from their patients as normal. A Yale research assistant will then test a small portion of the sample with an instant urine toxicology test.

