## 9.2 SAMPLE SIZE DETERMINATION

We plan to recruit a sample of 6 matched pair clusters (total of 12 clusters), with 6 clusters per condition and 20 patients per cluster for a total of 264 patients. Hypothesizing that CC will perform better than ECHO, this sample size achieves 80% power to detect a clinically meaningful minimum difference of 0.20 between the CC proportion (0.94) and the ECHO proportion (0.74).

To estimate the sample size needed to test differences between models of care in the proportion of women retained in treatment at delivery using a permutation test, we used the method of Hayes and Bennett (1999) for matched-pair cluster randomized trials. Our null hypothesis is  $p_{ECHO} = p_{CC}$  and the alternate hypothesis is  $p_{ECHO} \neq p_{CC}$ , where  $p$  is the proportion of women retained in treatment at delivery, setting a two-sided type 1 error rate of 0.05. We based the estimate of the proportion in the CC on a study by our co-investigator in which 94% of patients treated under a CC model continued MAT until delivery.

We could not find empirical data for an estimate of the coefficient of variation, so we followed the approach of Hayes and Bennett (1999). We generated 10,000 data sets with 6 clusters each, with true proportions assumed uniformly distributed between 0.72 and 0.99 to allow for a relatively wide range of plausible retention proportion values. In each of the simulated data sets coefficient of variation values were calculated based on formula (9) in the manuscript. This follows the conservative approach

suggested on p.322 of the paper (i.e. to use the coefficient of variation between clusters within each group as an upper limit for the coefficient of variation in matched pairs designs). After examining the distribution of the resulting coefficient of variation we selected 0.10 as the value for our subsequent power calculations since more than 90% of the data sets had values under that threshold.

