### 9.4 STATISTICAL ANALYSES

#### 9.4.1 GENERAL APPROACH

We will follow CONSORT guidelines, modified for cluster randomized trials, for reporting the trial ([www.consort-statement.org](http://www.consort-statement.org))(IR-5). Plans for data analysis will follow the major aims articulated above (IR-1) and the matched-pain cluster-randomized study design. We will examine the distribution of variables through descriptive statistics and graphical tools to verify that model assumptions are met to assess relationships between variables. Data analyses will use the intent-to-treat principle and we will attempt to follow all participants regardless of their retention to treatment. Dropouts (MD-3) and completers will be compared on baseline characteristics. Missingness (MD-2,4) will be examined for quantity, type (missing completely at random versus missing at random or not missing at random), and pattern (monotone, or non-monotone). If missing data are a significant issue, we will use sensitivity analyses (MD-4) and multiple

imputation methods that are appropriate for clustered data to fill in missing values in order to minimize bias, maximize available information and get accurate estimates of uncertainty. The possible impact of missing data on interpretation will be discussed in reports.

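### Section 9.4.4 tests baseline differences between care models at patient level although centres were randomised, so its p-values are too small if women within a site are alike

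*Combined protocol and SAP*

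**What the plan says.** Section 9.4.4 compares the two care models on demographic and clinical characteristics at baseline. Differences "will be assessed using chi-square tests for categorical variables and t-tests for continuous variables", with non-parametric counterparts where normality fails. It mentions neither site nor any correction for clustering, and it gives no significance level.

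Section 4.1 sets the design: "The unit of randomization is the obstetrical center". Section 9.2 plans 12 clusters, "with 6 clusters per condition and 20 patients per cluster for a total of 264 patients", and section 4.1 gives the split as "132 women from the CC sites and 132 from the ECHO sites".

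Elsewhere the plan allows for clustering. The primary models in 9.4.2 include a random site effect, because women at the same site may be positively correlated, and they add small-sample corrections. Section 9.4.3 applies the same approach to secondary patient outcomes. Section 9.4.6 uses random site effects even in exploratory subgroup models. Section 9.4.1 commits to CONSORT as modified for cluster trials.

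**The concern.** Chi-square tests, t-tests and their usual rank-based counterparts assume independent observations. Here the arm is a property of the site, so the comparison between arms is a comparison of six sites with six. If women at one site resemble each other more than women at different sites, the patient-level standard error is too small and chance differences are flagged too often. Section 9.4.4 is the exception within a plan that expects such correlation in its other comparisons between arms.

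At stake is the reading of the baseline table. A reader would take a small p-value as evidence that the arms differ by more than chance, when ordinary variation between sites may be enough to produce it.

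**Working it through.** **Is there a figure to reproduce?** No. The documents give no error rate, ICC or design effect for the baseline tests. The check therefore asks how far the true false-positive rate could sit from the nominal one.

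**Inputs from the documents**
- 12 sites, 6 per arm, 264 women, 132 per arm (9.2, 4.1).
- Women per site: 12 × 20 = 240, not 264, while 264 / 12 = 22. Section 5.5 gives an average of 20 per site with 10% attrition allowed for, and 264 × 0.90 = 237.6, or about 20 per site. A baseline table counts all enrolled women, so 22 is the main case and 20 a variant.
- Two sites with one participant each, and highly variable site sizes (9.4.2). No other site sizes are given.

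**Assumptions**
- Nominal level of 5%, two-sided. Section 9.2 speaks of "setting a two-sided type 1 error rate of 0.05", but for the sample size only.
- ICC from 0.01 to 0.20. None is given for baseline variables. For the retention outcome, section 9.2 says "We could not find empirical data for an estimate of the coefficient of variation".
- Enrolment at the target of 264. With fewer women per site the inflation would be smaller.

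**Formulas.** For average site size m, the design effect is DE = 1 + (m − 1) × ICC. A test that ignores clustering has true level 2 × [1 − Φ(1.96 / √DE)]. For unequal sites, m is replaced by Σm² / Σm.

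**Example at ICC 0.05 and m = 22.** DE = 1 + 21 × 0.05 = 2.05; 1.96 / √2.05 = 1.37; the true level is 17.1%.

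| ICC | DE (m = 22) | False positives, 22 per site | 20 per site | Illustrative unequal sites |
|---|---|---|---|---|
| 0.01 | 1.21 | 7.5% | 7.2% | 8.7% |
| 0.02 | 1.42 | 10.0% | 9.5% | 12.5% |
| 0.05 | 2.05 | 17.1% | 16.0% | 22.2% |
| 0.10 | 3.10 | 26.6% | 25.0% | 33.6% |
| 0.20 | 5.20 | 39.0% | 37.1% | 46.8% |

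The unequal case takes sites of 1, 10, 15, 25, 35 and 46 in each arm (sum 132; Σm² = 4292; 4292 / 132 = 32.5). These sizes are illustrative. Only the existence of two one-participant sites comes from the plan, which does not say which arms they are in.

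**Simulation with no true difference** (6,000 runs per setting, 22 per site, ICC 0.01, 0.02, 0.05, 0.10, 0.20):
- Patient-level t-test: 7.5%, 9.8%, 17.7%, 27.3%, 40.5%.
- Patient-level chi-square, for a characteristic with 37% prevalence: 7.4%, 10.7%, 18.1%, 26.9%, 41.1%.
- t-test on site means, 6 against 6: between 4.8% and 5.4%. With illustrative unequal sizes that include one-participant sites it gave 2.8% to 4.7%.

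**Borrowing the plan's own between-site variation.** For the coefficient of variation in the retention calculation, "we selected 0.10 as the value for our subsequent power calculations". For a proportion p, a coefficient of variation k implies ICC = k² × p / (1 − p). With k = 0.10 and 22 per site:
- p = 0.37: ICC 0.006, false positives 6.4%.
- p = 0.74: ICC 0.028, 12.1%.
- p = 0.94: ICC 0.157, 34%.

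That value was chosen for retention and not for any baseline variable, so this shows only how widely the answer can move.

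**The case against.** The strongest defence is that 9.4.4 is descriptive and nothing formal hangs on it. That largely stands. Section 9.4.2 names its fixed effects: the intervention for engagement and retention, and the intervention plus baseline PAM for the PAM score. Nothing in the plan lets baseline p-values choose covariates or alter an outcome model.

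A second defence is section 9.4.7, which says that analysis is at site rather than individual level. This does not repair 9.4.4. It does not mention baseline, it sits badly with the individual-level mixed models of 9.4.2, and it does not turn the named tests into site-level tests.

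Some stronger readings are tempting, but the documents do not support them:
- A reader might infer a fixed multiplier, such as false imbalances two to six times too often. At 22 per site that range (10% to 30%) needs ICCs of about 0.02 to 0.12, and the documents supply none.
- A reader might see the table as the trial's check for selective recruitment, because site staff enrol women after the sites are randomised (5.5, 6.2.1). The plan does not give it that role.
- A reader might call every flagged difference false. Because women are recruited after site randomisation, a real difference is possible.
- A reader might extend the point to section 9.4.1, where "Dropouts (MD-3) and completers will be compared on baseline characteristics". That comparison is not between arms and names no test. Dropout also varies within sites, so these figures do not carry over.

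**Conclusion.** The point holds as a limited inconsistency. Section 9.4.4 specifies patient-level tests for a comparison that was randomised at site level, and those tests reject too often whenever the baseline ICC is above zero. Under the stated assumptions the false-positive rate runs from about 7.5% at ICC 0.01 to 39% at ICC 0.20 with 22 women per site, against a nominal 5%. Under the illustrative unequal sizes it runs from 8.7% to 46.8%. The direction is certain once women within a site are positively correlated. The size depends on an ICC, a significance level for these tests and site sizes that the documents do not give. The consequence is confined to the baseline table and its interpretation, so this is a minor point that is still worth correcting.

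**What to change.** Reword 9.4.4 in one of two ways.

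1. Preferred: report baseline characteristics descriptively by arm and by site, without p-values. No error rate then arises. This does not separate a real imbalance from chance variation between sites, and the text should not suggest that it does. Standardised differences, if added, have the same limit.
2. If tests are kept: use ones that respect the site as the unit. For continuous and binary characteristics, use the 9.4.2 mixed model with a random site effect and its small-sample corrections. Where that model is not specified, for example for multi-category variables such as race/ethnicity, use a site-level comparison. State the significance level.

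The first option costs only a change of wording. The second needs a little extra programming, because 9.4.2 covers binary and continuous outcomes but not multi-category variables. Neither needs new data, and neither alters the outcome analyses.

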#### 9.4.5 PLANNED INTERIM ANALYSES

N/A

**9.4.6 SUB-GROUP ANALYSES**

To evaluate heterogeneity of effects we will report estimates of proportion and means together with 95% confidence intervals for each site. Due to feasibility constraints (only 12 sites) and lack of effect size estimates, we will not be able to perform a rigorous statistical evaluation of the effects of site level factors. However, we will present descriptive analyses of the sites that might be useful in guiding future use of the proposed models.

In addition, we will provide descriptive and exploratory analyses to evaluate heterogeneity of treatment effects on subject-level outcomes due to individual-level covariates including age, race/ethnicity, parity, illicit substances vs non-medical use of opioid prescriptions and concurrent substance use. We will use mixed effects statistical models to account for potential positive correlations among observations within sites (by including random site effects) and fixed effects of the intervention and potential covariates at the individual level. Interactions between treatment and potential moderating factors will be considered. Generalized linear mixed models will be used for categorical outcomes and linear mixed models for continuous outcomes.

**9.4.7 TABULATION OF INDIVIDUAL PARTICIPANT DATA**

Data will be analyzed at the site not individual level.

**9.4.8 EXPLORATORY ANALYSES**

Exploratory analyses will compare care models for eligible women (gravidas with an OUD, not in treatment when presenting for prenatal care) on the following outcomes: 1) #/% offered MAT including buprenorphine, specifically; and 2) rates of abstinence from illicit opioids or misuse of prescription opioids. (107) Additionally, for all pregnant women treated with MAT: 3) #/% continuing MAT at 3 months postpartum; 4) #/% engaging in an opioid treatment program at 3 months post-delivery. We will also explore differences between care models in: 5) #/% with concurrent substance use according to the **Time Line Follow-Back (TLFB)** (107) and urine tests; 6) fetal and neonatal outcomes (low birth weight, resuscitation at delivery, fetal demise, preterm birth, duration of hospitalization).

Exploratory analyses will also compare models in terms of participant reported differences in: 1) the **Shared-Decision Making Questionnaire-9 (SDM-Q-9)** (108); 2) **Perceived efficacy in Patient-Physician Interactions Questionnaire (PEPPI)** (109); 3) Kim Alliance Scale-Communication subscale (**KAS-CM**) (110); 4) PROMIS Emotional Short Form(111) and Satisfaction with Roles and Activities(111); and 5) **Edinburgh Postnatal Depression Scale (EPDS)**(112, 113) .

We will explore racial and ethnic differences on patient measures and possible differences in outcomes among those who were users of illicit street opioids vs misusers of prescription opioids.

**10 SUPPORTING DOCUMENTATION AND OPERATIONAL CONSIDERATIONS****10.1 REGULATORY, ETHICAL, AND STUDY OVERSIGHT CONSIDERATIONS****10.1.1 INFORMED CONSENT PROCESS**

#### 10.1.1.1 CONSENT/ASSENT AND OTHER INFORMATIONAL DOCUMENTS PROVIDED TO PARTICIPANTS

Consent forms describing in detail the study intervention, study procedures, and risks will be given to the participant and written documentation of informed consent will be completed prior to any research procedures taking place.

#### 10.1.1.2 CONSENT PROCEDURES AND DOCUMENTATION

The DSP at each site will confirm informed consent. Participants will be allowed as much time as necessary to read, understand and ask questions about the study and research procedures. Consent will take place in a private room.

#### 10.1.2 STUDY DISCONTINUATION AND CLOSURE

This study may be temporarily suspended or prematurely terminated if there is sufficient reasonable cause. Written notification, documenting the reason for study suspension or termination, will be provided by the suspending or terminating party to study participants, investigator, funding agency, and regulatory authorities. Study participants will be contacted, as applicable, and be informed of changes to study visit schedule.

Circumstances that may warrant termination or suspension include, but are not limited to:

- Determination of unexpected, significant, or unacceptable risk to participants
- Demonstration of efficacy that would warrant stopping
- Insufficient compliance of study staff to the protocol (i.e., significant protocol violations)
- Data that are not sufficiently complete and/or evaluable
- Determination that the primary endpoint has been met
- Determination of futility

The study may resume once concerns about safety, protocol compliance, and data quality are addressed, and satisfy the funding agency, sponsor, IRB, or other relevant regulatory or oversight bodies.

#### 10.1.3 CONFIDENTIALITY AND PRIVACY

Participant confidentiality and privacy is strictly held in trust by the participating investigators, their staff, the safety and oversight monitor(s), and the sponsor(s) and funding agency. This confidentiality is extended to the data being collected as part of this study. Data that could be used to identify a specific study participant will be held in strict confidence within the research team. No personally-identifiable information from the study will be released to any unauthorized third party without prior written approval of the sponsor/funding agency.

All research activities will be conducted in as private a setting as possible.

The study participant's contact information will be securely stored at each clinical site for internal use during the study. At the end of the study, all records will continue to be kept in a secure location for as long a period as dictated by the reviewing IRB, Institutional policies, or sponsor/funding agency requirements.

Study participant research data, which are for purposes of statistical analysis and scientific reporting, will be transmitted to and stored at Yale University. Individual participants and their research data will be identified by a unique study identification number whenever possible. The study data entry and study

management systems used by clinical sites and by Yale's research staff will be secured and password protected. At the end of the study, all study databases will be de-identified and archived at the Yale.

#### Certificate of Confidentiality

To further protect the privacy of study participants, the Secretary, Health and Human Services (HHS), has issued a Certificate of Confidentiality (CoC) to all researchers engaged in biomedical, behavioral, clinical or other human subjects research funded wholly or in part by the federal government. We will apply for a CoC given the nature of our population.

